7.3 Withdrawal of informed consent

Subjects may voluntarily withdraw consent to participate in the study for any reason at any time. Withdrawal of consent occurs only when a subject:

- Does not want to participate in the study anymore, and
- Does not allow further collection of personal data

In this situation, the investigator should make a reasonable effort (e.g. telephone, e-mail, letter) to understand the primary reason for the subject's decision to withdraw his/her consent and record this information.

Study treatment must be discontinued and no further assessments conducted, and the data that would have been collected at subsequent visits will be considered missing.

Further attempts to contact the subject are not allowed unless safety findings require communicating or follow-up.

All efforts should be made to complete the assessments prior to study withdrawal. A final evaluation at the time of the subject's study withdrawal should be made as detailed in the Assessment Schedule ([Table 8-1](#)).

Novartis will continue to keep and use collected study information (including any data resulting from the analysis of a subject's samples until the time of withdrawal) according to applicable law.

For US and Japan: All biological samples not yet analyzed at the time of withdrawal may still be used for further testing/analysis in accordance with the terms of this protocol and of the informed consent form.

For EU and RoW: All biological samples not yet analyzed at the time of withdrawal will no longer be used, unless permitted by applicable law. They will be stored according to applicable legal requirements.

7.4 Lost to follow-up

For patients whose status is unclear because they fail to appear for study visits without stating an intention to discontinue or withdraw, the investigator should show "due diligence" by documenting in the source documents steps taken to contact the subject, e.g. dates of telephone calls, registered letters, etc. A patient cannot be formally considered lost to follow-up until his/her scheduled end of study visit would have occurred.

7.5 Study Stopping rules

The severity of adverse events will be graded by the study site Investigator (or designee) based on clinical judgment and captured in the CRF AE page. This information will be used to quantify events that may lead to patient's discontinuation or stopping dose arms or the study.

The study will be placed on hold pending full review of all available clinical safety data and discussion with the Investigator if any of the following occur and may be stopped or amended based on the outcome of the full safety review.

- One patient on study drug experiences any adverse event that is CTCAE Grade 4 or higher that is classified as related to study drug.
- Two or more patients on study drug experience a similar adverse event that is a CTCAE Grade 3 or higher other than ALT elevation.
- The Principal Investigator and the Sponsor consider that the number and/or severity of adverse events justify discontinuation of the study.
- The Sponsor unilaterally requests it.

Safety reviews for study stopping will be conducted jointly between medically qualified representatives of the Sponsor and Investigator and a joint decision will be made.

7.6 Early study termination by the sponsor

The study can be terminated by Novartis at any time for any reason. This may include reasons related to the benefit/ risk assessment of participating in the study, practical reasons (including slow enrollment), or for regulatory or medical reasons. Should this be necessary, patient must be seen as soon as possible and treated as a prematurely discontinued patient. The investigator may be informed of additional procedures to be followed in order to ensure that adequate consideration is given to the protection of the patient's interests. The investigator will be responsible for informing IRBs/IECs of the early termination of the trial.

8 Procedures and assessments

8.1 Assessment schedule

Subjects should be seen for all visits/assessments as outlined in the assessment schedule or as close to the designated day/time as possible.

Missed or rescheduled visits should not lead to automatic discontinuation. Subjects who prematurely discontinue the study for any reason should be scheduled for a visit as soon as possible, at which time all of the assessments listed for the final visit will be performed. At this final visit, all dispensed investigational product should be reconciled, and the adverse event and concomitant medications recorded on the CRF.

Table 8-1 Assessment Schedule

Epoch	SCREENING	Baseline	Treatment											EOS ²	Follow up Phone call
Visit Name	Screening	Baseline	Treatment											EOS	
Visit Numbers ¹	1	101	201 ³	202 ³	203 ³	204 ³	205 ³	206					207 ³	399	
Days	-44 to -16	-15 to -1	1	7	14	28	42	56					84	112	142
Time (post-dose)	-	-	0h	-	-	-	0h	0h ³	1h	2h	4h	6h	0h	-	
Informed consent ⁴	X														

Commercially Confidential Information

Inclusion / Exclusion criteria	X	X													
Medical history/current medical conditions	X														
Demography	X														
Alcohol Test and Drug Screen	X	X													
Hepatitis and HIV Screen	X														
Pregnancy and assessments of fertility ⁶	X		X			X		X					X	X	
Physical Examination	X	X				X		X					X	X	
Body Temperature	X	X	X	X	X	X	X	X					X	X	
Body Height	X														
Body Weight	X	X	X	X	X	X	X	X					X	X	
Waist and hip circumference	X	X	X										X	X	
BMI	X	X	X	X	X	X	X	X					X	X	
waist:hip ratio	X	X	X										X	X	
Blood Pressure and Pulse Rate ⁷	X	X ⁸	X	X	X	X ⁸	X	X ⁸					X ⁸	X	
ECG evaluation	X	X											X	X	
Blood chemistry	X	X		X	X	X		X					X	X	

Epoch	SCREENING	Baseline	Treatment											EOS ²	Follow up Phone call
Visit Name	Screening	Baseline	Treatment											EOS	
Visit Numbers ¹	1	101	201 ³	202 ³	203 ³	204 ³	205 ³	206					207 ³	399	
Days	-44 to -16	-15 to -1	1	7	14	28	42	56					84	112	142
Time (post-dose)	-	-	0h	-	-	-	0h	0h ³	1h	2h	4h	6h	0h	-	

Commercially Confidential Information

Hematology	X	X		X	X	X		X					X	X	
Urinalysis	X	X			X	X		X					X	X	

Commercially Confidential Information

Coagulation Panel ¹⁰	X	X												X	
---------------------------------	---	---	--	--	--	--	--	--	--	--	--	--	--	---	--

Commercially Confidential Information

PK blood collection					X	X	X	X	X	X	X	X	X		
---------------------	--	--	--	--	---	---	---	---	---	---	---	---	---	--	--

Commercially Confidential Information

Dose administration			X ¹⁴												
---------------------	--	--	-----------------	--	--	--	--	--	--	--	--	--	--	--	--

Commercially Confidential Information

MRI ¹⁶		X											X	X ¹⁷	
Comments	As required														
Concomitant therapies	X ¹⁸														
Study completion information														X	
Adverse Events	As required														X
Serious Adverse Events	As required														X

¹ Visit structure given for internal programming purpose only

² If a patient withdraws from the study, or if study medication is discontinued for any reason, the patient should be scheduled for a subsequent visit at which time all assessments at the EOS visit should be performed.

³ All assessments to be performed pre-dose

⁴ Informed consent must be provided by all patients before any screening procedures are performed. Commercially Confidential Information

Commercially Confidential Information

⁶ Serum pregnancy tests will be performed at Screening and end of study; urine tests may be used at other timepoints.

⁷ Blood pressure and pulse rate will be measured in a sitting position unless otherwise noted.

⁸ Measured in sitting and standing positions to assess orthostatic hypotension.

Commercially Confidential Information

¹⁰ Coagulation panel includes PT/INR and aPTT

Commercially Confidential Information

¹⁴ Patients will be provided with a supply of study medication to self administer once daily for 12 weeks (Day 2 to Day 84). Patients should bring all used and unused medications, and diaries, to each visit.

Commercially Confidential Information

¹⁶ MRI of abdomen and liver in all subjects. Quantification of liver fat will be performed on all subjects;

Commercially Confidential Information

¹⁷ Assessment is only to be performed at EOS if a patient withdraws from the study, or discontinues study treatment early for any reason.

¹⁸ A thorough review of any concomitant medications (including medication name, dose, unit, frequency, and route) should be performed at every visit.

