7.2 Discontinuation of study treatment

Discontinuation of study treatment for a patient occurs when study treatment is stopped earlier than the protocol planned duration. Discontinuation of study treatment can be decided by either the subject or the investigator.

Study treatment must be discontinued under the following circumstances:

- Patient decision - patients may choose to discontinue study treatment for any reason at any time.
- The investigator believes that continuation would negatively impact the safety of the patient or the risk/benefit ratio of trial participation.
- Any protocol deviation that results in a significant risk to the patient's safety
- Pregnancy (see [Section 8.6](#) (Safety) and [Section 9.6](#) (Pregnancy reporting))
- Discontinuation may be considered when patients have to be treated by prohibited medications on a case by case basis.

- Use of prohibited treatment as per recommendations in [Table 5-1](#)
- Hypersensitivity (CTCAE grade 2 or higher) reaction to LIK066 requiring intervention.
- Clinically significant diarrhea, suspected to be related to the study drug and not responsive to recommended management per SOM that may put the patient at risk (identified by investigator after consultation with the sponsor)
- Symptomatic orthostasis confirmed by repeated orthostatic blood pressure changes (more than a 20 mmHg drop in systolic or 10 mmHg drop in diastolic blood pressure and increase in heart rate >20 bpm (compared to sitting results) when blood pressure and pulse are taken after at least 3 minutes (standing)
- Clinically significant urinary tract or genitourinary infections, at the discretion of the investigator and consultation with the sponsor
- Clinically symptomatic hypoglycemia confirmed by repeated blood glucose levels (<56 mg/dL)
- Ketoacidosis (symptoms of ketoacidosis include nausea, vomiting, abdominal pain, unusual tiredness and trouble breathing) confirmed by blood pH and ketones.
- For ALT, AST, total bilirubin and/or alkaline phosphatase elevations mandating study treatment discontinuations, please refer to [Section 9.3](#) and [Table 9-1](#) and [Table 9-2](#) for further instructions and monitoring. Of note, ALT and AST are abnormal at baseline in this study. Thus only elevation to >2X of the baseline value will trigger events listed in [Section 9.3](#).
- Adverse events, abnormal laboratory values or abnormal test result that indicate a safety risk to the patient, in the opinion of the investigator

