8.5.6 Liver function tests

ALT, AST, GGT, ALP (total), total bilirubin, and albumin will be assessed as indicated in the [Assessment schedule](#). The effect on circulating ALT levels will be the primary efficacy variable for this study.

If the total bilirubin concentration is increased above 1.5 times the upper limit of normal, direct and indirect reactive bilirubin will be quantified.

ALP isoenzymes and 5'NT will also be measured but will not form part of the screening requirements or safety data set.

The methods for assessment and recording are specified in the laboratory manual. Some of the liver function tests may be completed as part of the blood chemistry panel.

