9.3 Liver safety monitoring

To ensure patient safety and enhance reliability in determining the hepatotoxic potential of an investigational drug, a standardized process for identification, monitoring and evaluation of liver events has to be followed. The following two categories of laboratory abnormalities and AEs have to be considered during the course of the study 1) Liver laboratory triggers which will require repeated assessments of the abnormal laboratory parameter and 2) Liver events which will require close observation, follow up monitoring, and the completion of the standard base liver eCRF pages.

Please refer to [Table 9-1](#) for complete definitions of liver events.

Table 9-1 Liver Event Definitions

	Definition/ threshold
Liver laboratory triggers	
 ALT or AST $\geq 2 \times$ baseline value $1.5 \times \text{ULN} < \text{TBL} < 2 \times \text{ULN}$
Liver events	
 ALT or AST $> 5 \times \text{ULN}$ ALP $> 2 \times \text{ULN}$ (in the absence of known bone pathology) TBL $> 2 \times \text{ULN}$ (in the absence of known Gilbert syndrome) ALT or AST $> 3 \times \text{ULN}$ and INR $> 1.5 \text{ ULN}$ Potential Hy's Law cases (defined as ALT or AST $> 3 \times \text{ULN}$ and TBL $> 2 \times \text{ULN}$ [mainly conjugated fraction] without notable increase in ALP to $> 2 \times \text{ULN}$) Any clinical event of jaundice (or equivalent term) ALT or AST $> 3 \times \text{ULN}$ accompanied by (general) malaise, fatigue, abdominal pain, nausea, or vomiting, or rash with eosinophilia Any adverse event potentially indicative of a liver toxicity*

*These events cover the following: hepatic failure, fibrosis and cirrhosis, and other liver damage-related conditions; the non-infectious hepatitis; the benign, malignant and unspecified liver neoplasms

TBL: total bilirubin; ULN: upper limit of normal

Follow-up of liver events

Every liver event defined in [Table 9-1](#) should be followed up by the investigator or designated personnel at the trial site, as summarized below. Additional details on actions required in case of liver events are outlined in [Table 9-2](#).

For liver laboratory triggers

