- Repeating liver chemistry tests (ALT, AST, TBL, PT/INR, ALP and GGT) to confirm elevation within the next 7 days. If any of the lab tests described in [Table 9-1](#) are abnormal, all tests should be repeated. These liver chemistry repeats should preferentially be performed using the central laboratory, with the results provided via the standard electronic transfer. If results will not be available from the central laboratory within 24 hours, then the repeats can also be performed at a local laboratory to monitor the safety of the patient. If a liver event is subsequently reported, any local liver chemistry tests previously conducted that are associated with this event should have results reported on the unscheduled local laboratory CRF.
- If the initial elevation is confirmed, close observation of the patient will be initiated, including consideration of treatment interruption if deemed appropriate.

For Liver Events

- Discontinuation of the investigational drug (refer to [Section 7.2](#) (Discontinuation of study treatment), if appropriate)
- Hospitalization of the patient if appropriate
- Causality assessment of the liver event

Thorough follow-up of the liver event should include:

- Repeating liver chemistry tests to confirm elevation as appropriate. Testing should include PT/INR ALT, AST, ALP, and GGT. If total bilirubin is elevated > 2 x ULN, fractionation into direct and indirect bilirubin is required. To rule out muscular origin of transaminase elevations, CPK should be measured along with liver chemistry tests. Frequency of retesting should be done once a week if abnormalities stabilize or the study drug has been discontinued and the subject is asymptomatic. Retesting should be continued up to resolution or stabilization as described above.
- Obtaining a more detailed history of symptoms and prior or concurrent diseases.
- Obtaining a history of concomitant drug use (including nonprescription medications and herbal and dietary supplement preparations), alcohol use, recreational drug use, and special diets.
- Exclusion of underlying liver disease, as specified in [Table 9-3](#).
- Imaging such as abdominal US, CT or MRI, as deemed appropriate by the investigator
- Obtaining a history of exposure to environmental chemical agents.
- Considering gastroenterology or hepatology consultation.

All follow-up information, and the procedures performed must be recorded as appropriate in the CRF.

Table 9-2 Actions required for Liver Events

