Criteria	Actions required	Follow-up monitoring
Potential Hy's Law case ^a	
 • Discontinue the study drug immediately • Hospitalize, if clinically appropriate • Establish causality • Complete liver CRF 	ALT, AST, TBL, Alb, PT/INR, ALP and GGT until resolution ^c (frequency at investigator discretion)
ALT or AST		
> 10 × ULN	
 • Repeat within 48 hr • If elevation persists, discontinue drug • Hospitalize if clinically appropriate • Establish causality • Complete liver CRF 	ALT, AST, TBL, Alb, PT/INR, ALP and GGT until resolution ^c (frequency at investigator discretion)

Criteria	Actions required	Follow-up monitoring
> 3 × ULN AND INR > 1.5	
 Discontinue the study drug immediately Hospitalize, if clinically appropriate Establish causality Complete liver CRF 	ALT, AST, TBL, Alb, PT/INR, ALP and GGT until resolution ^c (frequency at investigator discretion)
> 5 to ≤ 10 × ULN	
 Repeat LFT within 1 week If elevation persists continue follow up, If elevation persists for more than 3 weeks discontinue drug Establish causality Complete liver CRF 	ALT, AST, TBL, Alb, PT/INR, ALP and GGT until resolution ^c (frequency at investigator discretion)
> 3 × ULN AND accompanied by symptoms ^b	
 Discontinue the study drug immediately Hospitalize if clinically appropriate Establish causality Complete liver CRF 	ALT, AST, TBL, Alb, PT/INR, ALP and GGT until resolution ^c (frequency at investigator discretion)
> 3 to ≤ 5 × ULN if normal baseline or >2 × baseline if elevated before drug exposure (patient is asymptomatic)	
 Repeat LFT within 1 week If elevation is confirmed, initiate close observation of the subject 	Investigator discretion Monitor LFT within 1 to 4 weeks
ALP (isolated)		
> 2 × ULN if normal baseline (in the absence of known bone pathology)	
 Repeat LFT within 48 hours If elevation persists, establish causality Complete liver CRF 	Investigator discretion Monitor LFT within 1 to 4 weeks or at next visit
TBL (isolated)		

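### The raised-INR liver criterion has two different thresholds, and for a narrow group of patients no visible text requires the on-treatment INR that it needs

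*Protocol*

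**What the plan says.** All references are to the Protocol.

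- **The criterion.** Section 9.3, Table 9-1 lists ALT or AST above 3 × ULN with INR above 1.5 ULN as a liver event. The matching row of Table 9-2 ends "ULN AND INR > 1.5", with no ULN after the 1.5, and calls for immediate discontinuation of study drug.
- **The schedule.** Table 8-1 has a separate row, "Coagulation Panel ¹⁰", whose footnote reads "Coagulation panel includes PT/INR and aPTT". It is marked at screening, baseline and the end-of-study visit (Day 112). The row "Blood chemistry", which includes ALT and AST according to Section 8.6.3, is also marked on Days 7, 14, 28, 56 and 84.
- **The liver test list.** Section 8.5.6 states "ALT, AST, GGT, ALP (total), total bilirubin, and albumin will be assessed as indicated in the" assessment schedule. INR is not in that list.
- **Reflex testing.** After a laboratory trigger (ALT or AST at least 2 × baseline, or bilirubin between 1.5 and 2 × ULN), Section 9.3 asks for "Repeating liver chemistry tests (ALT, AST, TBL, PT/INR, ALP and GGT) to confirm elevation within the next 7 days". Follow-up of any liver event also includes PT/INR.
- **The note on raised baselines.** Section 7.2 observes that transaminases are abnormal at entry and concludes "Thus only elevation to >2X of the baseline value will trigger events listed in" Section 9.3.
- **Entry limits.** Section 4.2 excludes ALT or AST above 8 × ULN and INR above 1.3.

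**The concern.** Two separate problems meet in one safety criterion.

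First, the table that defines the event and the table that prescribes the action use different INR limits. Sites working from different tables could classify the same patient differently, and so differ on stopping treatment and on completing the liver event pages.

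Second, this population is selected for raised ALT, so a patient can satisfy the transaminase half of the criterion from the first dose. INR then decides alone. The other laboratory values in Table 9-1 (ALT, AST, ALP and bilirubin) are in the on-treatment chemistry panel. INR is the only one with no visible scheduled on-treatment measurement.

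**Working it through.** No sample size or power figure bears on this point. The check is threshold arithmetic and a reading of the schedule.

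**1. The two INR limits.** Let U be the laboratory's INR ULN. The documents do not give it, so a range is assumed. The Table 9-1 limit is 1.5 × U; the Table 9-2 limit is 1.5.

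| Assumed U | 1.5 × U | INR that meets Table 9-2 only |
|---|---|---|
| 1.0 | 1.50 | none |
| 1.1 | 1.65 | above 1.50, up to 1.65 |
| 1.2 | 1.80 | above 1.50, up to 1.80 |
| 1.3 | 1.95 | above 1.50, up to 1.95 |

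Entry INR may be as high as 1.3. If INR is the single value using the 10% allowance in Section 4.2, it may be 1.3 × 1.1 = 1.43. The distance from entry to 1.5 can therefore be as small as 0.20 (1.5 − 1.3) or 0.07 (1.5 − 1.43).

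**2. Scheduled measurements in the visible rows of Table 8-1.**

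| Row | Before dosing | On treatment, after first dose | End of study |
|---|---|---|---|
| Blood chemistry (ALT, AST) | screening, baseline | Days 7, 14, 28, 56, 84 | Day 112 |
| Coagulation (PT/INR) | screening, baseline | none | Day 112 |

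INR accompanies 0 of the 5 on-treatment chemistry draws. The baseline window is Day −15 to Day −1 and there is no Day 0, so the interval to Day 112 is 112 to 126 days, or 16 to 18 weeks. It contains all 84 treatment days. Day 112 is 28 days after the last planned dose.

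**3. When reflex INR starts.** Let b be baseline ALT or AST in multiples of ULN. Under Table 9-1, transaminases alone lead to PT/INR at 2b (laboratory trigger) or above 5 × ULN (liver event), whichever is lower. The uncovered band therefore runs from just above 3 to min(2b, 5) × ULN. If the Section 7.2 sentence governs instead, the upper end is 2b.

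| b | 2b | Uncovered band, Table 9-1 | Upper end if Section 7.2 governs |
|---|---|---|---|
| 1.5 | 3 | none | none |
| 2 | 4 | 3 to 4 | 4 |
| 2.5 | 5 | 3 to 5 | 5 |
| 4 | 8 | 3 to 5 | 8 |
| 8 | 16 | none: already above 5 | 16 |

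A patient with b between 3 and 5 can stay in the band with stable values. One with b between 1.5 and 3 must rise into it. In either case the patient must also lack every other route to PT/INR: bilirubin above 1.5 × ULN, ALP above 2 × ULN, the listed symptoms with transaminases above 3 × ULN, jaundice, or an adverse event suggesting liver toxicity.

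**4. Section 7.2 against Table 9-1.** Table 9-1 defines its transaminase events in multiples of ULN, without reference to baseline. Section 7.2 makes a rise beyond twice baseline a condition for Section 9.3 events. Read literally, that condition would suppress the event above 5 × ULN, and the raised-INR event itself, in a patient who has not doubled.

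**The case against.** The strongest reply is that INR by reflex is a legitimate design. Section 9.3 calls for PT/INR after either laboratory trigger and after any liver event, including ALT or AST above 5 × ULN and above 3 × ULN with symptoms. Table 9-2 has a row for transaminases raised before drug exposure, so high baselines were considered. Patients also enter without cirrhosis and with limits on INR and albumin. This stands, and it confines the gap to the band above. It does not close the band: for a patient with raised baseline, that Table 9-2 row acts only beyond twice baseline.

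A reader might go further and infer that the criterion cannot operate on treatment at all, that many patients are affected, or that a patient entering at 4 × ULN gets no INR until 8 × ULN. The documents do not support these readings. The reflex routes do operate on treatment, and no baseline ALT distribution is given. Under Table 9-1 that patient becomes a liver event above 5 × ULN; 8 × ULN applies only if Section 7.2 overrides the table and no other trigger occurs.

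Three textual replies remain:

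- **Section 8.6.6** mentions INR under Hematology, whose row is marked on Days 7, 14, 28, 56 and 84. But Section 8.6 leaves timing to the schedule, which gives coagulation its own row.
- **Redaction.** Parts of Table 8-1 are hidden. The primary baseline in Section 11.4.1 uses a Day 1 ALT that the visible chemistry row does not show, so a hidden row may carry liver tests. A hidden INR cannot be ruled out, although the coagulation row is visible and the Section 8.5.6 list omits INR.
- **Footnote 2 of Table 8-1** brings the end-of-study assessments, hence INR, forward after early discontinuation. That is after the decision the criterion should inform.

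The threshold difference could be a slip of wording. Even so, it leaves two limits for one action.

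**Conclusion.** The point holds in two parts.

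The threshold conflict is the firmer part. It is visible in the text and does not depend on the schedule. Only its size rests on an assumption: an INR ULN of 1.1 to 1.2 gives a zone of disagreement from 1.5 up to 1.65 to 1.80, and it vanishes only at a ULN of exactly 1.0.

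The schedule part is real but narrow. With no visible on-treatment INR, the criterion cannot detect an INR rise in an asymptomatic patient with ALT or AST of about 3 to 5 × ULN, below twice baseline and without any bilirubin, ALP or other trigger. If Section 7.2 governs, the band extends to twice baseline, at most 16 × ULN for entry at the 8 × ULN limit. How many patients fall in the band cannot be derived from the documents, and the finding is limited to the unredacted schedule.

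**What to change.** Reconcile the INR threshold between Tables 9-1 and 9-2. Reconcile Table 8-1 with Sections 7.2, 8.6.6 and 9.3, so that the INR data the criterion needs exist when it is meant to act. The text should also settle whether the twice-baseline sentence in Section 7.2 limits the events in Table 9-1, and whether the INR in Section 8.6.6 follows the Hematology or the coagulation row. The choice of threshold and timing belongs to the clinical team.

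The cost is a short amendment and a note to sites. If the team decides on additional INR measurements, they could use chemistry draws that already take place, at the price of one small tube each.
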